### 8.1 Replacement of Subjects

At the Sponsor's discretion, the number of subjects who are enrolled may be increased to account for early dropouts if the dropout rate is projected to be greater than 10%.

## **9 STUDY TERMINATION BY FIBROGEN**

FibroGen has the right to terminate this study or to close any site at any time.

FibroGen may also suspend enrollment temporarily at any time for business or other reasons.

If the planned interim analysis indicates a lack of efficacy, FibroGen will terminate the Extended Treatment Period and dosing will cease for all subjects.

## 10 STATISTICS

### 10.1 Sample Size Determination

This study is planned to enroll approximately 136 subjects, which will include a target of 110 subjects who are seeking first-line therapy and 26 subjects who failed pirfenidone and/or nintedanib treatment. First-line therapy is defined as no prior therapy with pirfenidone/nintedanib or <10% relative decrease in FVC % predicted while receiving either pirfenidone or nintedanib. Failure of pirfenidone and or nintedanib treatment is defined as having  $\geq 10\%$  relative decrease in FVC % predicted during prior pirfenidone/nintedanib treatment. The effect of first-line treatment is the primary interest of the study, and is the basis for sample size determination. Assuming a 10% dropout rate and a common standard deviation of 7.3, a sample size of 55 subjects per arm in the primary analysis population provides approximately 80% power to detect a treatment difference of 4.2 in change from baseline to Week 48 in percent predicted FVC, using a two-sample t-test at the two-sided significance level of 0.05. The expected treatment difference is estimated using data from study FG-3019-049 and placebo data from published studies. In Study FG-3019-049, a mean decline of 2.8 in % predicted FVC from baseline to Week 48 was observed. The expected decline of 7.0 % predicted FVC in the placebo arm is estimated based on the weighted average of published studies ([Azuma, 2005](#), [Daniels, 2010](#), [Demedts, 2005](#), [King, Jr., 2008](#), [King, Jr., 2009](#), [King, Jr., 2011](#), [Meier-Kriesche, 2004](#), [Noble, 2011](#), [Noth, 2012](#), [Raghu, 2004](#), [Raghu, 2008](#), [Raghu, 2012](#), [Richeldi, 2011](#), [Taniguchi, 2010](#), [Zisman, 2010](#)).

Second line therapy patients are evaluated in an exploratory fashion. If the treatment effect in the pirfenidone/nintedanib failure group is similar to that in the general population, the two subgroups will be combined to achieve higher power.

### 10.2 Analysis Populations

#### 10.2.1 Safety Population

The Safety Population will consist of all randomized subjects who received any dose of study medication. If actual treatment received differs from the randomized treatment arm, the actual treatment arm will be used for safety data analysis.

#### 10.2.2 Full Analysis Set Population

The Full Analysis Set (FAS) Population will consist of randomized subjects who received at least one dose of study drug and have evaluable FVC assessments at baseline and at least one evaluable post baseline. The FAS population will be used in the primary analyses of the PFT endpoints and other efficacy endpoints except for PFS.

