##### **3.2.2 Secondary Efficacy Endpoints.**

- Change in pulmonary fibrosis score by quantitative HRCT at Week 24, Week 48, and later time points.
- Change from baseline in HRQoL at Week 24, Week 48, and later time points.
- Progression of IPF, defined as time from Day 1 to any one of the following:
  - Death from any cause
  - Absolute decline in FVC % of predicted value of  $\geq 10\%$  not due to intercurrent illness, confirmed by repeat spirometry.
  - Clinical diagnosis of IPF progression.
- Proportion of subjects with at least one respiratory-related hospitalization.
- Proportion of subjects with respiratory-related death, censored at Week 52.
- Categorical assessment of absolute change from baseline in FVC percent of predicted value at Week 48.

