### **10.3.4 Efficacy Analyses**

The primary efficacy analyses will be performed in subjects in the FAS population except for analyses of PFS, which will be based on the Safety Population. Rules of missing data imputation will be described in the SAP. Analyses based on observed data will be used for sensitivity analyses.

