#### **10.3.4.1 Primary Efficacy Analysis**

The primary analysis will be to compare the treatment arms in change from baseline to Week 48 in FVC % predicted based on the FAS Population. A rank ANCOVA model will be used, with baseline FVC % predicted value as covariate, treatment group, stratification, and treatment by stratification interaction as fixed effects. Factors may be eliminated from the model if they are insignificant. If the interaction term is significant, the primary analysis will be based on the subgroup of subjects on first-line therapy.

The ranks of the primary endpoint will be based on observed data and on imputed data if observed data are not available. A detailed description of the rank assessment will be described in the statistical analysis plan. A repeated measures model utilizing all observed data will be used for sensitivity analysis.

Descriptive summaries of the primary efficacy parameter will include the following:

1. Median change from baseline by treatment and visit
2. % of subjects with no decline by treatment and visit
3. % of subjects with decline  $\geq 10\%$  by treatment and visit

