#### **10.4 Statistical Analysis Plan**

The SAP will include detailed plans for presenting and analyzing study data, as well as documentation of changes in protocol-specified analysis plans.

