3.2.5 TEAE and Mortality

TEAE and mortality will be reported in percentage per total number of subjects exposed.

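### Respiratory-related death and hospitalisation are assigned to a set that requires a post-baseline FVC, so an early event can remove the very subject who had it

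*Protocol*

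**What the plan says.** Protocol 10.2.2 sets three entry conditions for the FAS: at least one dose, an evaluable baseline FVC and an evaluable post-baseline FVC ("have evaluable FVC assessments at baseline and at least one evaluable post baseline"). Its scope is broad: "The FAS population will be used in the primary analyses of the PFT endpoints and other efficacy endpoints except for PFS". Section 10.2.3 gives HRCT scores a separate set, and 10.3.4.3 analyses PFS in the Safety Population, which has no FVC condition.

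Protocol 3.2.2 lists among the secondary efficacy endpoints "Proportion of subjects with respiratory-related death, censored at Week 52" and "Proportion of subjects with at least one respiratory-related hospitalization". Neither is PFS or an HRCT score, so both fall on the FAS.

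Appendix 1 schedules spirometry at Day 1 and Weeks 12, 24, 36 and 48. No post-baseline FVC is therefore scheduled before Week 12.

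For the primary endpoint, 10.3.4.1 runs the rank ANCOVA on the FAS and adds: "The ranks of the primary endpoint will be based on observed data and on imputed data if observed data are not available". Section 10.3.4 says "Rules of missing data imputation will be described in the SAP". The SAP supplied is Part 2, on the extension. Its introduction places the randomised-period analyses in Part 1, which is not among the documents.

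**The concern.** Whether a subject belongs to the FAS depends on something that happens after randomisation. For FVC endpoints that is a familiar compromise. For a count of respiratory deaths or hospitalisations it serves no purpose, because a subject can be classified on either endpoint without any spirometry. It can also do harm: a respiratory death at Week 8, with no FVC since Day 1, takes the subject out of the analysis that is meant to count that death.

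The removal need not be balanced between arms. These endpoints may rest on few events in about 68 subjects per arm (136/2), so one or two removals can change the visible comparison. The protocol already avoids the problem for PFS, where the same Week 8 death counts as an event.

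**Working it through.** **1. The plan's own power figure.** Inputs from Protocol 10.1: 55 per arm, 10% dropout, SD 7.3, difference 4.2, two-sided 0.05. Evaluable subjects: 55 × 0.90 = 49.5 per arm. Standardised difference: 4.2/7.3 = 0.575. Two-sample t-test power is 80.9%, which agrees with the stated figure of about 80%. The sample size is not in dispute, and this figure does not bear on which subjects enter the two proportion endpoints.

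**2. Following one subject through the text.** Take a dosed subject who dies of respiratory failure at Week 8 with no FVC after Day 1.

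| Analysis | Set | Counted? |
|---|---|---|
| Respiratory-related death (3.2.2) | FAS | No |
| Respiratory-related hospitalisation (3.2.2), if it preceded the death | FAS | No |
| Primary rank ANCOVA (10.3.4.1) | FAS | No, unless SAP Part 1 changes this |
| PFS (10.3.4.3) | Safety Population | Yes |
| SAE reporting (10.3.5, 11.2.2) | Dosed subjects | Yes |

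**3. How many subjects.** The documents give no early loss rate. If the planned 10% dropout is spread evenly over 48 weeks, the number leaving before Week 12, for any reason and in both arms together, is:

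- 110 × 0.10 × 12/48 = 2.75 first-line subjects;
- 136 × 0.10 × 12/48 = 3.4 of all subjects.

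If half of the dropout falls before Week 12, the figure is 136 × 0.05 = 6.8; if all of it does, 13.6. Leavers who give an end-of-treatment FVC stay in the FAS.

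**4. Respiratory deaths.** Assume D deaths per arm by Week 52, each falling before Week 12 with probability 12/52 = 23%, and none of those subjects giving an FVC. The number removed per arm is Binomial(D, 12/52). P(at least one removed) = 1 − (40/52)^(2D).

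| D per arm | Mean removed per arm | At least one removed | Unequal by arm | Gap of 2 or more |
|---|---|---|---|---|
| 2 | 0.5 | 65% | 52% | 6% |
| 4 | 0.9 | 88% | 66% | 20% |
| 8 | 1.8 | 98% | 76% | 37% |

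The 23% is an approximation and can err either way:

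- A true constant hazard with 4/68 deaths gives [1 − (64/68)^(12/52)]/(4/68) = 23.6%.
- Risk concentrated early gives more.
- Sections 7.4 and 7.5 let a missed spirometry move to the next visit, so a first FVC can come after Week 12.
- Eligibility criteria and earlier unscheduled spirometry push the figure down.

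In rates, a true tie of 4/68 against 4/68 (5.9% each) becomes 3/67 (4.5%) against 4/68 (5.9%) if one FG-3019 death is removed. It becomes 2/66 (3.0%) against 4/68 (5.9%) if two are removed on FG-3019 and none on placebo; that split has probability 6.6%.

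No comparable figure can be given for hospitalisation. A subject hospitalised early who later gives an FVC stays in the set.

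**5. Primary test, subject to SAP Part 1.** Simulated Mann-Whitney test, means −2.8 and −7.0, SD 7.3, 20,000 trials per case, no covariate or later dropout. Three early losses are split between arms by chance (3/0, 2/1, 1/2, 0/3 with weights 1/8, 3/8, 3/8, 1/8).

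| Handling of the three losses | 55 per arm | 68 per arm |
|---|---|---|
| Excluded (FAS) | 82% | 89% |
| Given the placebo mean | 81% | 89% |
| Ranked worst | 79% | 87% |

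Averaged over splits, the choice moves power by 1 to 3 points. For a particular split it can move more: at 55 per arm, worst rank gives about 62% for 3/0 (FG-3019/placebo) and 91% for 0/3.

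With no true effect and 55 per arm, take the extreme case in which the excluded subjects are exactly the lowest-ranked of their arm. The FAS test then favours FG-3019 in about 4% of trials (1/0), 5 to 6% (2/0) or just under 8% (3/0), against 2.5% nominal. At 68 per arm the 3/0 figure is about 7%.

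**The case against.** The strongest case against is that nothing disappears from the trial. All-cause death is a PFS event in the Safety Population, deaths and inpatient hospitalisations are SAEs, and 10.3.1 lists all randomised subjects. That is right, and it limits the point to two secondary proportions in a Phase 2 study. It does not repair them. The planned comparison of categorical endpoints would still run on the depleted set, and hospitalisation is not a PFS component.

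SAP Part 1 may also define the populations differently. It may, since Protocol 10.4 says the SAP will contain the detailed analysis plans "as well as documentation of changes in protocol-specified analysis plans". But that would be a change from what the protocol now says, and the protocol wording would still need to match.

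Four stronger readings are tempting but not supported:

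- **The primary test is biased.** A reader might infer this because imputation within the FAS cannot bring back a subject outside it. But imputation and ranking are deferred to the SAP, average power hardly moves, and the test stays valid if loss does not depend on arm. The raised error rates need an extreme pattern of loss. The worst-rank results answer a combined FVC-and-death question, so they do not show a fault in the FAS.
- **The SAP contradicts the protocol.** SAP 3.2.5 says "TEAE and mortality will be reported in percentage per total number of subjects exposed". This is a descriptive safety denominator in the extension plan. It supports the fix by analogy only.
- **Early stoppers give no FVC.** Section 4.2.4.1 asks everyone who stops before Week 48 for an end-of-treatment visit, and Appendix 3 includes spirometry in it. Section 8, however, makes those efficacy assessments discretionary, and Appendix 3 footnote a refers to subjects with more than 4 doses. Doses at Weeks 0, 3, 6 and 9 make four, so with no missed doses that wording passes over those who stop before Week 12. The gap is uncertain, not complete.
- **A Day 1 test can stand in for the end-of-treatment spirometry.** Appendix 3 footnote b might be read this way. Its context is withdrawal evaluations already done, so the reading is strained and nothing here rests on it.

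**Conclusion.** The point holds for respiratory-related death and respiratory-related hospitalisation. On the protocol's wording, both are analysed in a set that can exclude a subject because of the event being counted. It should be fixed, but the effect is probably small: a few subjects at most under the planned dropout, and material only if early losses are unbalanced between arms. The 88% and 66% figures rest on an assumed 4 deaths per arm and the 12/52 approximation; the documents supply neither.

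For the primary test this is a query to be settled against SAP Part 1. The documents do not establish a defect there.

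**What to change.** 1. State in 10.2.2 and 10.3.1 that respiratory-related death and hospitalisation are analysed in all randomised, dosed subjects, by randomised arm. These are the subjects of the Safety Population already used for PFS. The arm must be named because 10.3.1 now summarises efficacy by treatment actually received.
2. If SAP Part 1 does not already do so, add a sensitivity analysis of the primary endpoint in all randomised, dosed subjects with a baseline FVC, by randomised arm. Pre-specify the rank or imputation for those with no post-baseline FVC. Whether deaths take the worst rank is the sponsor's choice and should be stated, because it changes the question the test answers.
3. Reconcile section 4.2.4.1, section 8, Appendix 1 footnote j and Appendix 3 footnote a on end-of-treatment spirometry for early stoppers in both arms.

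The cost is a few sentences and at most one added analysis. Results may look slightly less favourable if early losses cluster on FG-3019. The change does not by itself recover events after AE collection ends, 4 weeks after the last dose (11.3.1), although the death endpoint runs to Week 52.

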#### 10.2.3 HRCT Evaluable Population

The HRCT Evaluable (HE) Population will consist of randomized subjects who have evaluable HRCT fibrosis scores at baseline and at Week 24 or at a later time point. The HE population will be used in the analyses related to HRCT fibrosis scores.

## **10.3 Statistical Analysis**

### **10.3.1 General Analysis Methods**

Unless the planned interim analysis at the end of the Randomized Treatment Phase indicates a lack of efficacy, the study is completed when the last subject completes the last visit in the Extended Treatment Phase.

Baseline characteristics, safety, and biomarker data will be summarized based on available data in the Safety Population, except for the parameters indicated otherwise. The primary efficacy analyses will be based on the FAS population, except for the analysis of PFS, which will be based on the Safety Population. All safety, efficacy, and exploratory endpoints will be summarized by group of actual treatment received.

All randomized subjects will be included in the data listings.

Continuous variables will be presented by descriptive statistics: n, mean, standard deviation, or standard error, median, minimum, and maximum. Categorical variables will be presented by counts of subjects and percentage.

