
Statistical Methods:
	
This study is planned to enroll approximately 136 subjects, who will include a target of 110 subjects who are seeking first-line therapy and approximately 26 subjects who failed pirfenidone and/or nintedanib treatment. First line therapy is defined as no prior therapy with pirfenidone and/or nintedanib or <10% relative decrease in FVC % predicted while receiving either pirfenidone or nintedanib. Pirfenidone and/or nintedanib failure is defined as having <math>\geq 10\%</math> relative decrease in FVC % predicted during prior pirfenidone and/or nintedanib treatment. The effect of first-line treatment is the primary interest of the study and is the basis for sample size estimates. Assuming a 10% dropout rate and a common standard deviation of 7.3, a sample size of 55 subjects per arm in the primary analysis population provides approximately 80% power to detect a treatment difference of 4.2 in change from baseline to Week 48 in percent predicted FVC, using a two-sample t-test at the two-sided significance level of 0.05. If the treatment effect in the pirfenidone and/or nintedanib treatment failure group is similar to that in the general population, the two subgroups will be combined to achieve higher power.
 
The primary efficacy analysis is to compare the treatment arms in change from baseline to Week 48 in FVC % predicted. A rank ANCOVA model will be used. A repeated measures model utilizing all observed data will be used for sensitivity analyses. Logistic regression and Fisher’s exact test will be used to compare categorical endpoints. The Cox regression model will be used in time-to-event endpoints. All efficacy and safety data will be summarized descriptively by treatment arm.

	Treatment effect will be evaluated in various subgroups of interest. Unblinded analyses will be performed after all subjects have either completed the Week 48 assessments or discontinued the study.
--	---

This study will be conducted in accordance with the guidelines of Good Clinical Practice (GCP) and the applicable regulatory requirement(s), including the archiving of essential documents.

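### Protocol 10.3.1 summarises efficacy by treatment actually received, which conflicts with the protocol's own randomised-arm comparisons; the effect is probably small and one sentence fixes it

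*Protocol*

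**What the plan says.** Protocol 10.3.1 (General Analysis Methods) sets one grouping rule for every type of endpoint: "All safety, efficacy, and exploratory endpoints will be summarized by group of actual treatment received".

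Other parts of the protocol differ:

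- **10.2.1, Safety Population:** "If actual treatment received differs from the randomized treatment arm, the actual treatment arm will be used for safety data analysis". The rule is given for safety data and nothing else.
- **Synopsis, Statistical Methods:** "All efficacy and safety data will be summarized descriptively by treatment arm".
- **10.3.4.1, Primary Efficacy Analysis:** the task is to "compare the treatment arms in change from baseline to Week 48 in FVC % predicted". Section 10.3.4.3 likewise compares treatment arms for progression-free survival. Section 4.2 uses the term for the two groups formed by 1:1 randomisation.
- **10.2.2, Full Analysis Set:** "The Full Analysis Set (FAS) Population will consist of randomized subjects who received at least one dose of study drug", with FVC requirements added. This says who is included, not how they are grouped.

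For the extension, SAP Part 2 (3.2.1 and 4.3) defines efficacy by original randomised arm. Subjects randomised to FG-3019 keep their study-entry baseline; placebo subjects who roll over get a new one. SAP Part 2 Section 4 rules out formal inference.

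**The concern.** Grouping safety by treatment received is normal practice. Extending it to efficacy is not, because a subject who is regrouped by what was infused is no longer in the group that randomisation assigned.

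The practical problem is a mismatch inside one set of results. Section 10.3.4.1 asks for the rank ANCOVA between arms and also for descriptive summaries by treatment and visit: median change, percentage with no decline, and percentage with a decline of at least 10%. Under 10.3.1 those summaries would use actual treatment, while the model they accompany would use the randomised arm. If even one subject were mis-dosed, the denominators and medians could disagree with the analysis.

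The rule is also incomplete. Study drug comes in coded vials and is given 16 times in the randomised period. The protocol does not say which group a subject belongs to after a mixture of correct and incorrect infusions.

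**Working it through.** **Step 1. Set the grouping rules side by side.**

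| Place | Applies to | Grouping |
|---|---|---|
| Protocol 10.3.1 | safety, efficacy, exploratory (summaries) | actual treatment |
| Protocol 10.2.1 | safety data | actual treatment |
| Protocol Synopsis | efficacy and safety (summaries) | treatment arm |
| Protocol 10.3.4.1 | primary comparison | treatment arms |
| Protocol 10.3.4.3 | progression-free survival comparison | treatment arms |
| Protocol 10.2.2 | Full Analysis Set | not stated |
| SAP Part 2, 3.2.1 and 4.3 | extension efficacy | original randomised arm |

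For efficacy summaries, 10.3.1 and the Synopsis conflict for any subject whose actual and assigned treatments differ. No section states outright that efficacy is analysed as randomised. That has to be inferred from the word arms and its use in Section 4.2.

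**Step 2. Reproduce the plan's power.** Inputs from Protocol 10.1: difference 4.2, SD 7.3, 55 per arm, 10% dropout, two-sample t-test, two-sided 0.05.

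- Evaluable per arm: 55 × 0.9 = 49.5.
- Noncentrality: 4.2 / (7.3 × √(2/49.5)) = 2.86.
- Power: 80.9% by the noncentral t distribution, 81.7% by the normal approximation.

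The stated figure of approximately 80% is reproduced. It does not depend on the grouping rule.

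**Step 3. Count the subjects who could be affected in the randomised period.** The documents give no mis-dosing rate. Assume 0-3%: 0.03 × 136 = 4.1, so 0 to 4 subjects. The placebo crossover adds none, because Section 4.2.6 offers it only after the 48-week period.

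**Step 4. Price the as-randomised rule.** Assume a fraction f of each arm receives the other arm's treatment throughout, and hold the SD at 7.3. The as-randomised difference becomes 4.2 × (1 − 2f).

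| f per arm (assumed) | Difference | t-test power, 49.5 per arm |
|---|---|---|
| 0 | 4.20 | 80.9% |
| 1% | 4.12 | 79.3% |
| 2% | 4.03 | 77.7% |
| 5% | 3.78 | 72.3% |

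At the top of the assumed range, 3%, the difference is 4.2 × 0.94 = 3.95, and power lies between the last two rows. This is a pessimistic case, since it supposes the wrong treatment at every infusion.

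**The case against.** The strongest reply is that 10.3.1 speaks of summaries, while the sections that define the inferential comparisons refer to arms. A specific section normally prevails over a general one, so the tests of the primary endpoint and progression-free survival are most naturally read as randomised comparisons. This stands. A reader might infer from 10.3.1 that the primary test itself is as-treated; the documents do not support that.

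Second, analyses of the randomised period are documented in Part 1 of the SAP, which was not available, and Protocol 10.4 leaves detailed plans and changes to the SAP. Part 1 may already settle the grouping. This also stands, although the protocol sentence would still need to be reconciled with it.

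Third, a stronger reading is tempting for the extension. The HRCT secondary endpoint is "Change in pulmonary fibrosis score by quantitative HRCT at Week 24, Week 48, and later time points", HRQoL runs equally late, and all placebo subjects are offered FG-3019 after Week 48. A reader might conclude that 10.3.1 pools those who switch with Arm A. No section plans this. SAP Part 2 defines the two origins separately, with different baselines, so that the effect of active treatment can be evaluated separately from placebo. The extension is also descriptive only. What remains is that SAP 4.5 and 5.6 do not restate the grouping for the displays.

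Nor does 10.3.1 remove the placebo group after Week 48. The crossover design does that, and grouping by randomised arm would not restore an untreated comparator.

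**Conclusion.** The inconsistency is real: the only sentence that expressly says how efficacy endpoints are grouped by treatment received or assigned uses treatment received, against 10.2.1, the Synopsis and the arm comparisons in 10.3.4.1 and 10.3.4.3. Its consequence is limited to efficacy and exploratory summaries for mis-dosed subjects, on an assumed rate 0 to 4 of 136. No effect on the primary comparison is shown, and the placebo switch cannot reach the Week 48 endpoint. The conclusion rests on reading arms as randomised arms, on the assumed mis-dosing range, and on the absence of SAP Part 1. It is worth correcting because the correction is nearly free and removes any doubt about whether efficacy follows randomisation.

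**What to change.** Replace the sentence in Protocol 10.3.1 with: *Safety endpoints will be summarised by actual treatment received. Efficacy and exploratory endpoints will be analysed and summarised by randomised arm.* Check that SAP Part 1 says the same.

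For consistency with SAP Part 2 Sections 3.2.1 and 4.3, add: *After Day 1-EX, efficacy will be shown separately by original randomised arm.* This confirms the SAP's evident intent; it does not correct a stated plan to pool.

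The cost is a short text change with no new data. If subjects are mis-dosed, the as-randomised estimate is slightly diluted, as Step 4 of the working shows (power about 79.3% at an assumed 1% per arm). That is the accepted price of keeping the randomised comparison.
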